^b Subjects will receive an alert through the eDiary if their GSRS scores reach the appropriate threshold. This alert will tell the subject to begin taking the randomized study treatment the same day. At this time, study site should arrange the Week 0 Visit as soon as possible after the first administration of randomized study treatment. Visit dates will be measured from the first administration of randomized study treatment.

^c This visit may be performed remotely if more convenient for the subject; site must telephone the subject to document concomitant medications/procedures and AEs.

^d The safety follow-up will be performed as a telephone interview 2 weeks (±5 days) after the Week 10/ET visit.

^e GI symptom and eDiary compliance assessment.

^f Including height and weight measurements and vital signs (temperature, blood pressure, and sitting blood pressure).

^g Medical history, including MS disease status, will include collection of information on duration of MS, relapse history, EDSS score, and treatment for MS.

^h Dipstick test (only for women of childbearing potential).

CONFIDENTIAL

^j Serum, RNA, and DNA samples will be collected for biomarker analysis and future use analysis in subjects who provide additional consent. A single DNA sample can be taken at any of prespecified timepoints.

Version 3

^k Subjects will be required to record their daily GI symptoms in the eDiary every day from the Screening Visit up to Week 10.

¹ eDiaries will be returned if (1) the subject fails during the Screening Period, (2) the subject does not reach the required GI symptom threshold during the DMF-GI Monitoring Period, or (3) the subject completes or discontinues the study.

^m Subjects who do not reach the GI symptom threshold during the DMF-GI Monitoring Period (a GSRS score of ≥ 5 in 1 question for 1 day, ≥ 4 in 1 question for 2 consecutive days, or ≥ 3 in 1 question for 3 consecutive days) will be discontinued.

ⁿ Subjects are dispensed randomized study treatment at this visit but must not begin taking the medication until alerted about their eDiary.

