8.2. Exclusion Criteria

Candidates will be excluded from study entry if any of the following exclusion criteria exist at the Screening Visit or at the timepoint defined in the individual criterion listed:

- 1. Inability to comply with the study requirements or, at the discretion of the Investigator, is deemed unsuitable for study participation.
- 2. Female subjects who are currently pregnant or breastfeeding or who are considering becoming pregnant during the study.
- 3. History of significant GI disease (e.g., irritable bowel disease, peptic ulcer disease, history of major GI surgery, eosinophilic GI disease, or food allergies).
- Chronic use (≥7 consecutive days) of bismuth subsalicylate, simethicone, calcium carbonate, loperamide, proton-pump inhibitors, or ondansetron within 1 month prior to the Screening Visit. From Screening up to Day 10, use of such therapies is not permitted. From Day 11 (inclusive), subjects are permitted to take these therapies.
- 5. Use of the following medications: montelukast, immunotherapy, mast cell stabilizers, or parenteral, inhaled, or oral steroids up to 1 month prior to the Screening Visit. Use of these medications is also not permitted for the duration of the study (except for the use of montelukast as per study protocol) and will lead to discontinuation.
- 6. Treatment with montelukast is contraindicated for any reason.

CONFIDENTIAL

- 7. Exposure to fumarates in the 3 months prior to the Screening Visit. Exposure is also not permitted for the duration of the Screening Period.
- 8. Have 1 or more major comorbidities that, in the opinion of the Investigator, may affect the outcome of the study.
- 9. History of malignancy (except for basal cell carcinoma that had been completely excised prior to study entry), severe allergic or anaphylactic reactions or known drug hypersensitivity, abnormal laboratory results indicative of any significant disease, and/or a major disease that would preclude participation in a clinical study.
- 10. Prior confirmed diagnosis or medical history of chronic eosinophilia.
- 11. Current enrollment in any other interventional clinical studies.

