10.3.2. Symptomatic Therapy to Treat Dimethyl Fumarate-Related Gastrointestinal Events

From Day 10 onward, but not before, subjects may use the following medications: bismuth subsalicylate, simethicone, calcium carbonate, loperamide, proton-pump inhibitors, and ondansetron.

CONFIDENTIAL

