Average change of GI severity scores from Day 0 (baseline) to Week 10 will be calculated as the sum of changes from baseline in GSRS score over the first 10 weeks divided by the total number of days with GSRS recorded. This endpoint will be analyzed by the MMRM as in the analysis of the above endpoint. Sensitivity analyses using ANCOVA model for the average change may be performed. Trajectory plots of mean change and the model based estimated mean change from baseline in GSRS score (with 95% CIs), by time and by treatment group, will be presented.

Time to first worsening of GSRS in GI severity

The GI severity is worsened if the GSRS score increases from baseline (Day 0). Time to first worsening of GSRS in GI severity is defined as the number of days from Day 0 to the first date with a worsened GSRS score. If a patient does not experience any worsening from Day 0 to Day 10, his/her time to first worsening will be censored at Day 10 or the day of study treatment (Montelukast/PBO) discontinuation, whichever comes first.

Time to the first worsening of GSRS by treatment arm will be analyzed using the Kaplan-Meier method and the Cox's proportional hazards model adjusted for age, weight and baseline GSRS score. If the proportionality assumption does not hold, a log-rank test will be used.

Time to recovery to Day 0 GSRS score from the last occurrence of the worst score in GI severity

The GI severity is recovered to Day 0 GSRS score if the GSRS score is smaller than or equal to the Day 0 score. Time to recovery to Day 0 score from the last occurrence of the worst score is defined as the date of recovery minus the date of the last occurrence of the worst score. If a patient does not experience a worsening in GSRS score, the last occurrence of the worst score is Day 0 and time to recovery is 1. If a patient experiences a worsening of GSRS score but does not experience a recovery before Week 8, his/her time to recovery will be censored at Week 8 or the day of study treatment (Montelukast/PBO) discontinuation or the day of switching to other GI medications listed in I/E criterion 8, whichever comes first.

Time to recovery to Day 0 GSRS score from the last occurrence of the worst score will be analyzed using the Kaplan-Meier method and the Cox's proportional hazards model.

Average change of GSRS score from Day 0 to Week 1, 2, 3, 4, 5, 6 and 8

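### The time-to-recovery rule censors at GI medication only subjects who do not later recover, and the censoring date can fall before the time origin, so Kaplan-Meier recovery is biased upward within an arm

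*Combined protocol and SAP*

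**What the plan says.** SAP 7.3.4 defines recovery by the score alone: "The GI severity is recovered to Day 0 GSRS score if the GSRS score is smaller than or equal to the Day 0 score". Being off GI medication is not required. The time "is defined as the date of recovery minus the date of the last occurrence of the worst score". Subjects who never worsen are assigned a time of 1.

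The censoring sentence opens with a condition: "If a patient experiences a worsening of GSRS score but does not experience a recovery before Week 8". Only for those subjects does it continue: "his/her time to recovery will be censored at Week 8 or the day of study treatment (Montelukast/PBO) discontinuation or the day of switching to" one of the listed GI medications, whichever is earliest. The analysis is Kaplan-Meier and Cox.

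Three other places matter:

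- Protocol 10.3.2 on GI medication: "From Day 10 onward, but not before, subjects may use the following medications". Exclusion criterion 4 in Protocol 8.2 has a different first day: "From Day 11 (inclusive), subjects are permitted to take these therapies".
- Protocol Table 1, footnote k: "Subjects will be required to record their daily GI symptoms in the eDiary every day from the Screening Visit up to Week 10". Scores are therefore still collected after GI medication starts and after Week 8.
- The title of SAP Table 20 describes the worst score only as post-baseline. No search window is stated.

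**The concern.** Kaplan-Meier and Cox require that being censored at a given time does not depend on what happens to the subject later. Here it does. Whether GI medication ends a subject's time at risk is decided by whether recovery follows before Week 8. Time after medication is kept when it ends in recovery and deleted when it does not, which biases the estimate even if medication were taken at random.

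Separately, the origin (last day at the worst score) and the censoring date are set independently, and nothing makes the origin come first. The SAP has no rule for a negative time. If such records are dropped, only non-recoverers are lost.

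At stake are the recovery curves and hazard ratio for one secondary endpoint. SAP section 5 closes enrollment at about 60 dosed patients, so a few misplaced non-recoverers can move the curves. It also has group-level results reviewed once patients reach Day 10. An unstated window might then be chosen after results have been seen.

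**Working it through.** The documents give no figure for this endpoint, so there is none to reproduce. The check applies the written rule literally.

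**1. Dates.** Censored time = censoring date - origin.

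- Medication Day 12, last worst score Day 30, no recovery before Week 8: 12 - 30 = -18 days.
- No medication, last worst score Day 63, censored at Week 8 (Day 56): 56 - 63 = -7 days. This arises only if Weeks 8-10 are searched for the worst score.

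**2. Dependence on the later outcome, in miniature.** Take four worsened subjects with origin Day 8, all starting GI medication on Day 12. Two recover on Day 35 and two never do. Under the written rule the non-recoverers are censored at 12 - 8 = 4 days and the recoverers are events at 35 - 8 = 27 days. At 27 days two are at risk and two recover, so estimated recovery is 1 - (1 - 2/2) = 100%. In fact 2/4 = 50% recovered. The example is deliberately extreme.

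**3. Size in large samples.** Assumptions, none from the documents except the Week 8 limit and the first medication day:

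- recovery hazard *h* = 3% per day from the origin, Day *o*;
- GI medication starts at rate *m* per day from Day 10, unrelated to recovery and with no effect on it;
- negative times are dropped.

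The share starting medication by Week 8 (46 days, Day 10 to Day 55) is 1 - (1 - *m*)^46. The share not recovered before Day 56 is *q* = (1 - *h*)^(55 - *o*). At time *t* the fraction with an event is *h*(1 - *h*)^(*t* - 1). The fraction at risk under the written rule is

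*n*(t) = (1 - *h*)^(*t* - 1) - *q*[1 - *G*(t)], where *G*(t) = (1 - *m*)^(*o* + *t* - 10), or 1 if *o* + *t* < 10.

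The subtracted term is the deleted non-recovered time. With *m* = 4% and *o* = 20, *q* = 0.97^35 = 0.344. At *t* = 28, *G* = 0.96^38 = 0.212, so *n* = 0.439 - 0.344 x 0.788 = 0.168. The apparent hazard is 0.0132 / 0.168 = 7.8%, against a true 3%.

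Multiplying the daily terms gives 28-day recovery. The truth is 1 - 0.97^28 = 57.4%.

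| Start rate per day | Use by Week 8 | Origin Day 5 | Origin Day 8 | Origin Day 20 |
|---|---|---|---|---|
| 0.25% | 11% | 57.7% | 57.9% | 58.7% |
| 0.38% | 16% | 57.9% | 58.1% | 59.4% |
| 1% | 37% | 58.8% | 59.3% | 62.5% |
| 2% | 61% | 60.2% | 61.1% | 67.3% |
| 4% | 85% | 62.6% | 64.3% | 75.1% |

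The excess is 0.3 to 2.0 points at 11-16% use, the rate Protocol 5.2 reports from earlier DMF studies. At 85% use it is 5.2 to 17.7 points. With recovery at 10% per day and origin Day 5 or 8, it is at most 0.3 points even at 85% use.

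**4. Recovery by Week 8.** A simulation of 100,000 subjects with origin Day 8, true recovery 59% and medication unrelated to recovery gave 60.6%, 63.0%, 65.7% and 70.5% under the written rule at 10%, 25%, 40% and 60% use. Censoring every subject at medication returned 59.2% throughout.

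**5. Simulated diary paths.** Here daily scores were autocorrelated and medication depended on the score. With the worst-score search ending at Week 8, 7% to 62% of non-recoverers had negative times. With the search to Week 10 it was 64% to 89%. Recovery was quick in these paths, so the excess was only 0 to 3 points at 7 to 28 days.

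**The case against.** The best defence is that the sentence is ordinary shorthand: subjects without the event are censored at the end of observation. Time to first worsening is worded in a similar way. For stopping randomized treatment the defence largely works, because Protocol 12 withdraws such subjects and little is seen afterwards. It fails for GI medication, which does not end follow-up. The diary continues, and later recoveries are observed and counted.

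A reader might infer more than the documents support:

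- **That the bias is large.** The larger figures need 37% to 85% GI-medication use and a late origin. The only documented rate is 11-16%. This trial doses only subjects who reach a symptom threshold, so higher use is plausible, but no figure is given.
- **That the arm using more GI medication will look much better, or that montelukast is favoured.** An arm at 4% per day exceeds one at 1% by about 4 points (origin Day 5: 62.6 - 58.8) to 13 points (origin Day 20: 75.1 - 62.5) with no true difference. That compares 85% use with 37%. The documents do not say which arm will use more. If placebo does, a true montelukast benefit shrinks.
- **That negative times after Week 8 follow from the rule.** They depend on a search running to Week 10, which the SAP does not state. Week 8 is this endpoint's censoring limit and the end of randomized dosing, so a search ending there is a natural reading. The -18 day example does not depend on this.

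It is also fair to say that a common end date leaves an origin known only in hindsight, and that censoring at a drug taken for symptoms may itself be informative.

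**Conclusion.** The defect stands on the current text. Early censoring is conditional on not recovering later, and the censoring date may precede the origin. Both push estimated recovery upward within an arm.

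The size depends on GI-medication use, recovery speed and origin day, none of which the documents give for this population. Under 3% recovery per day and medication unrelated to recovery, the 28-day excess is about half a point to 2 points at 11-16% use and about 5 to 18 points at 85% use. It is small when recovery is fast. The effect on the treatment contrast follows the difference in GI-medication use between arms, and its direction is undetermined. One secondary endpoint is affected and the primary analysis is not. The correction should be made because it is cheap and the present rule cannot be programmed without unstated choices.

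**What to change.** In SAP 7.3.4:

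1. Define one end date for every subject, set without regard to later recovery: the earliest of Week 8, study-treatment discontinuation, first listed GI medication and last recorded GSRS.
2. Search for both the worst score and recovery only on or before that date, for recoverers and non-recoverers alike. Say that the same window decides who never worsened and so receives a time of 1.
3. State how a worst score on the end date itself (time zero) is handled.
4. Because GI medication is taken for symptoms, add a sensitivity analysis that follows everyone to Week 8 and either ignores GI medication or counts it as not recovered. An origin at first worsening would also avoid the hindsight origin.
5. Correct the pointer to the medication list. The SAP cites I/E criterion 8, which matches the synopsis numbering, but item 8 in Protocol 8.2 concerns comorbidities. The Day 10 and Day 11 statements on when these therapies are permitted must also be reconciled.

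The cost is SAP wording and derivation code, with no new data and no change in conduct. The downside is that recoveries after GI medication no longer count as events in the main analysis.

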12. WITHDRAWAL OF SUBJECTS FROM STUDY TREATMENT **AND/OR THE STUDY**

A subject *must* permanently discontinue study treatment and be withdrawn from the study for any of the following reasons:

- Failure to meet the required eDiary compliance criteria (\geq 75%) in the 14 days prior to randomization.
- Failure to meet the GSRS score criteria during the DMF-GI Monitoring Period. •
- The subject experiences a medical emergency that necessitates permanent discontinuation of study treatment.
- The subject uses prohibited concomitant medications (as outlined in Sections 1 and 10.3.1).
- The subject withdraws consent.

Protocol 109MS414

- At the discretion of the Investigator for medical reasons or for noncompliance.
- The subject has a concurrent illness or injury, or abuses alcohol or drugs to the extent that, in the judgment of the Investigator and/or Sponsor, it would affect assessments of clinical status to a significant degree.

The reason for discontinuation of study treatment and withdrawal from the study must be recorded in the subject's CRF.

Subjects who discontinue study treatment will be withdrawn from the study. Whenever possible, subjects who prematurely discontinue study treatment should complete an ET Visit (undergoing the same assessments as the Week 10 Visit).

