6 SAMPLE SIZE JUSTIFICATION

Assuming that 40% of the placebo subjects will be improving (by chance) without any intervention, a total sample size of 118 (dosed with randomized study treatment), 59 per treatment arm (after randomization), would provide approximately 80% power to detect a 30% difference between the treatment arm and placebo arm in proportion of subjects with any improvement in GI severity, as measured by the average change from Day 0 in GSRS score to Day 10. Power was estimated assuming a 15% early discontinuation rate.

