7 STATISTICAL ANALYSIS METHODS

The statistical software, SAS[®], will be used for all summaries and statistical analyses.

Summary statistics will be used throughout. For continuous endpoints, the summary statistics will generally include: the number of subjects with data, mean, standard deviation (SD), median, 25th and 75th percentile (Q1, Q3), minimum and maximum. For categorical endpoints, the summary statistics will generally include: number of patients randomized and dosed, the number of patients with data, and the number and percent of subjects with data in each category.

All statistical tests will be 2-sided with a type I error rate of 5%, unless otherwise specified.

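### Time to recovery is censored at GI medication or treatment stop, which probably overstates recovery, and as worded the censoring depends on whether the subject later recovers

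*Combined protocol and SAP*

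**What the plan says.** SAP 7.3.4 defines two time-to-event secondary endpoints.

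- **First worsening.** The event is the first day with a GSRS score above Day 0. Without such a day, "his/her time to first worsening will be censored at Day 10 or the day of study treatment" discontinuation, whichever is earlier. GI medication is not a censoring reason here.
- **Recovery.** The clock starts at the last occurrence of the worst score and stops when the score is back at or below Day 0. A subject who never worsens has a recovery time of 1. A subject who worsens and has no recovery before Week 8 is censored at Week 8, at the stop of montelukast/placebo, or at "the day of switching to other GI medications listed in I/E criterion 8, whichever comes first".

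Both use Kaplan-Meier and Cox models. The only fallback is a log-rank test for first worsening if hazards are not proportional. Tables 19 and 20 list no alternative handling of these censoring events.

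Protocol 12 adds: "Subjects who discontinue study treatment will be withdrawn from the study". Protocol 10.3.2 allows the listed GI medications from Day 10. GI symptomatic therapy and DMF discontinuation for GI events are themselves secondary endpoints, each compared by chi-squared test (SAP 2.2 and 7.3.4).

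**The concern.** Kaplan-Meier, Cox and log-rank methods all assume that a censored subject has the same later chance of the event as those still followed (for Cox, given the covariates). That is hard to defend for recovery. The listed drugs treat GI symptoms, so subjects who start them are mostly those who have not recovered, and many treatment stops will have the same cause. Censoring removes them from the risk set and lets faster recoverers represent them. Section 7.3.4 thus treats as uninformative the same kinds of event that it compares elsewhere as unfavourable outcomes.

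The wording raises a second problem. The censoring clause applies only to a worsened subject without recovery before Week 8. Diary entries continue to Week 10, so recovery after GI medication will be observed. Read literally, that recovery is an event, while a medicated subject who never recovers is censored back at the medication date. Whether a subject is censored then depends on what happens later.

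At stake are the recovery curve and its treatment comparison and, to a lesser degree, first worsening.

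**Working it through.** **The plan's own figure.** The documents give no power or event count for either endpoint. The only sample-size statement, "a total sample size of 118 (dosed with randomized study treatment), 59 per treatment arm (after randomization), would provide approximately 80% power", concerns the binary primary endpoint. For 40% vs 70%, two-sided 5% and 80% power, the two-proportion formula gives [1.96√(2×0.55×0.45) + 0.8416√(0.24+0.21)]²/0.30² = 42 per arm. With continuity correction this is 49, and 49/0.85 = 57.6, or 58 per arm (116 in total), close to 118. The censoring point does not depend on this.

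**Recovery: assumed inputs (none is in the documents).** Slow recoverers are 50% of placebo and 25% of montelukast subjects. The daily recovery hazard r is 0.08 (fast) or 0.01 (slow). The daily medication hazard m, from Day 10, is 0.005 (fast) or 0.05 (slow). Follow-up is 56 days from a common start.

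1. Recovered had nobody been medicated: 1 − exp(−56r) = 0.9887 (fast), 0.4288 (slow). Placebo: 0.5×0.9887 + 0.5×0.4288 = 70.9%. Montelukast: 0.75×0.9887 + 0.25×0.4288 = 84.9%.
2. Recovered before any medication: [1 − exp(−10r)] + exp(−10r)·r/(r+m)·[1 − exp(−46(r+m))] = 0.9651 (fast), 0.2364 (slow). Weighted: 60.1% and 78.3%.
3. Medicated before recovery: exp(−10r)·m/(r+m)·[1 − exp(−46(r+m))] = 0.0259 (fast), 0.7063 (slow). Weighted: 36.6% and 19.6%.
4. Kaplan-Meier with censoring at medication: 1 − exp(−∫h(t)dt), where h(t) is the mean recovery hazard among subjects neither recovered nor medicated at t.
5. Literal wording, assuming medication does not change recovery: as in step 4, but non-recoverers leave the risk set at medication and eventual recoverers stay in until they recover.

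The second block divides both medication hazards by five (13.9% vs 7.2% medicated).

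| Recovered by Week 8 | Placebo | Montelukast | Difference (points) |
|---|---|---|---|
| *36.6% vs 19.6% medicated* | | | |
| Nobody medicated | 70.9% | 84.9% | 14.0 |
| Kaplan-Meier, censored at medication | 79.2% | 91.8% | 12.6 |
| Before any medication | 60.1% | 78.3% | 18.2 |
| Literal wording | 89.6% | 95.0% | 5.5 |
| *13.9% vs 7.2% medicated* | | | |
| Nobody medicated | 70.9% | 84.9% | 14.0 |
| Kaplan-Meier, censored at medication | 72.2% | 86.2% | 14.1 |
| Before any medication | 67.6% | 83.0% | 15.4 |
| Literal wording | 74.6% | 87.2% | 12.7 |

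A simulation of 200,000 subjects per arm with the first set of hazards agreed to within about 1 point (36% vs 19% medicated).

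In the first block, Kaplan-Meier exceeds the no-medication figure by 8.3 and 7.0 points. The difference moves from 18.2 to 12.6 points, but 18.2 − 14.0 = 4.2 of that is the change of question and only 14.0 − 12.6 = 1.4 is informative censoring.

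**Estimand check.** Assume a 14-day median recovery in both arms, 46 days of follow-up, and censoring events unrelated to recovery in 5% vs 25%. Kaplan-Meier gives 90% in both arms, correctly for the no-medication question (1 − 2^(−46/14) = 0.90). Counting those events as not recovered gives 86% vs 70%. The two analyses differ even where censoring is uninformative.

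**First worsening: extreme bounds.** Take 60% vs 30% worsening, the complement of the planning rates, as an assumption. Suppose the 15% who discontinue (0.15×59 = 8.85, about 9 per arm) all stop at the start with no day above Day 0. If none of them would have worsened, the proportions are 0.60×0.85 = 51% and 0.30×0.85 = 25.5%. If all would have, add 15 points: 66% and 40.5%. The 30-point difference could then lie between 51 − 40.5 = 10.5 and 66 − 25.5 = 40.5 points.

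**The case against.** The strongest reply is that censoring at medication targets a legitimate quantity: recovery had nobody been medicated. Measured against that, the first block shows about 1.4 points lost from the difference, and in the same model the Cox hazard ratio is 1.53 with the SAP's censoring and 1.60 with medication counted as failure. This stands for the treatment comparison under the first reading of the rule. It does not rescue the arm-level proportions, or the literal wording.

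The assumed medication use is high beside the 11% to 16% in Protocol 5.2, and at 14% vs 7% the excess nearly vanishes. That too stands, although the historical figure covers all DMF-treated subjects, whereas everyone dosed here has already crossed a GI symptom threshold.

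The illustration simplifies the endpoint. The SAP starts the clock at the last worst score and gives never-worsened subjects an event at time 1, so fewer subjects are exposed to censoring than in the model. The figures are therefore illustrative only. GI medication and DMF discontinuation for GI events are also compared separately, so the failures are not hidden from the report.

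A reader might infer three stronger things, none of which the documents support. One is that the rule shrinks the montelukast effect: no medication or stop rates by arm are given, so the direction is unknown. Another is that a GI-related stop can never count as worsening: any earlier day above Day 0 is already an event, so only stops without such a day are lost. The third is that the primary result is affected: SAP 7.3.3 does not use this censoring.

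**Conclusion.** The concern holds for recovery and, in a limited way, for first worsening. If GI medication and treatment stops follow persisting symptoms, the planned Kaplan-Meier recovery proportions are too high. The excess over the no-medication figure runs from about 1 point per arm (14% vs 7% medicated) to 7 to 8 points (37% vs 20%), on assumed hazards. SAP 5 closes enrolment at about 60 dosed subjects, or 30 per arm if balanced, so 7 to 8 points is about two subjects per arm.

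The literal wording is the more serious defect: in the same model it gives 90% vs 95% against 71% vs 85%. The text does not settle which reading was intended.

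For first worsening the issue is confined to stops without an earlier day above Day 0. The bounds of 10.5 to 40.5 points are a worst case, not an expected bias.

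**What to change.** Change SAP 7.3.4 as follows.

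1. Reword the recovery rule so that what happens at GI medication or treatment stop does not depend on whether the subject later recovers.
2. Report recovery by cumulative incidence, with GI medication and GI-related stops as competing events, or equivalently keep those subjects as not recovered to Week 8. Keep the present censoring as a sensitivity analysis.
3. For first worsening, add a sensitivity analysis that counts a GI-related stop with no earlier day above Day 0 as a worsening on that day.
4. Replace the reference to criterion 8. It matches the synopsis numbering, but number 8 in Protocol 8.2 is major comorbidities.

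The cost is SAP wording and a few extra outputs. GSRS is recorded daily to Week 10 (SAP Table 1), GI medication is in the eDiary (SAP 7.2.8), and reasons for stopping are in the CRF (Protocol 12). Because subjects who stop are withdrawn, scores after a stop will mostly not exist. Defining the stop as an outcome avoids needing them.

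The downside is that recovery then means recovery without GI medication or a GI-related stop, which partly overlaps the separate medication and discontinuation endpoints. The SAP should say so.
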